9.6 Safety

9.6.1 Adverse events

9.6.1.1 Definitions

Definition of adverse event (AE)

In a clinical study, an AE is any untoward medical occurrence (i.e., any unfavorable and unintended sign [including abnormal laboratory findings], symptom, or disease) in a patient or clinical investigation subject after providing written informed consent for participation in the study. Therefore, an AE may or may not be temporally or causally associated with the use of a medicinal (investigational) product.

A surgical procedure that was planned prior to the start of the study by any physician treating the subject should not be recorded as an AE (however, the condition for which the surgery is required may be an AE).

In the following differentiation between medical history and AEs, the term "condition" may include abnormal physical examination findings, symptoms, diseases, laboratory, or ECG.

- Conditions that started before signing of informed consent and for which no symptoms or treatment are present until signing of informed consent are recorded as medical history (e.g., seasonal allergy without acute complaints).
- Conditions that started before signing of informed consent and for which symptoms or treatment are present after signing of informed consent, at unchanged intensity, are recorded as medical history (e.g., allergic pollinosis).
- Conditions that started or deteriorated after signing of informed consent will be documented as AEs. This includes intercurrent illnesses.

¹⁶⁴ Text modified for clarity (Amendment 1)

¹⁶⁵ Text modified as per amendment 4

	Integrated Clinical Study Protocol	
	BAY A2502/ 16027	
03 NOV 2020	Version 11.0	Page: 68 of 259

Definition of serious adverse event (SAE)

An SAE is classified as any untoward medical occurrence that, at any dose, meets any of the following criteria (a - f):

- a. Results in death
- b. Is life-threatening

The term 'life-threatening' in the definition refers to an event in which the subject was at risk of death at the time of the event, it does not refer to an event which hypothetically might have caused death if it were more severe.

c. Requires inpatient hospitalization or prolongation of existing hospitalization

A hospitalization or prolongation of hospitalization will not be regarded as an SAE if at least one of the following exceptions is met:

- The admission results in a hospital stay of less than 12 hours
- The admission is pre-planned
- (e.g., elective or scheduled surgery arranged prior to the start of the study; admission is part of the study procedures as described in Section 9.2)
- The admission is not associated with an AE (e.g., social hospitalization for purposes of respite care).

However, it should be noted that invasive treatment during any hospitalization may fulfill the criterion of 'medically important' and as such may be reportable as an SAE dependent on clinical judgment. In addition, where local regulatory authorities specifically require a more stringent definition, the local regulation takes precedence.

d. Results in persistent or significant disability/incapacity

Disability means a substantial disruption of a person's ability to conduct normal life's functions.

- e. Is a congenital anomaly/birth defect
- f. Is another serious or important medical event as judged by the investigator

9.6.1.2 Classifications for adverse event assessment

In part 1 of the study, all AEs will be assessed and documented by the investigator according to the categories detailed below.

In part 2 of the study, AEs considered at least possibly related to nifurtimox and AEs caused by protocol-required procedures will be assessed and documented by the investigator according to the categories detailed below.

9.6.1.2.1 Seriousness

For each AE, the seriousness must be determined according to the criteria given in Section 9.6.1.1.

9.6.1.2.2 Intensity

The intensity of an AE is classified according to the following categories:

- Mild: a type of AE that is usually transient and may require only minimal treatment or therapeutic intervention. The event does not generally interfere with usual activities of daily living.
- Moderate: a type of AE that is usually alleviated with additional specific therapeutic intervention. The event interferes with usual activities of daily living, causing discomfort, but poses no significant or permanent risk of harm to the subject.
- Severe: a type of AE that requires intensive therapeutic intervention. The event interrupts usual activities of daily living, or significantly affects clinical status. The event possesses a significant risk of harm to the subject and hospitalization may be required.¹⁶⁶

9.6.1.2.3 Causal relationship

The assessment of the causal relationship between an AE and the administration of treatment is a decision to be made by the investigator, who is a qualified physician, based on all information available at the time of the completion of the eCRF.

Causality should be assessed separately for each study treatment as detailed in the eCRF. If the investigator feels that the event cannot be firmly attributed to one of the study treatments (e.g., owing to a suspected underlying interaction), the same assessment will be documented for each study treatment.

The assessment is based on the question whether there was a "reasonable causal relationship" to the study treatment in question.

Possible answers are "yes" or "no"

An assessment of "no" would include:

1. The existence of a highly likely alternative explanation, e.g., mechanical bleeding at surgical site.

or

2. Non-plausibility, e.g., the subject is struck by an automobile when there is no indication that the drug caused disorientation that may have caused the event; cancer developing a few days after the first drug administration.

An assessment of "yes" indicates that the AE is reasonably associated with the use of the study treatment.

Important factors to be considered in assessing the relationship of the AE to study treatment include:

¹⁶⁶ Text added per Modification 7 (Amendment 1)

03 NOV 2020

- The temporal sequence from drug administration: The event should occur after the drug is given. The length of time from drug exposure to event should be evaluated in the clinical context of the event.
- Recovery on drug discontinuation (de-challenge), recurrence on drug re-introduction (re-challenge): Subject's response after de-challenge or re-challenge should be considered in view of the usual clinical course of the event in question.
- Underlying, concomitant, intercurrent diseases:
 Each event should be evaluated in the context of the natural history and course of the disease being treated and any other disease the subject may have.
- Concomitant medication or treatment: The other drugs the subject is taking or the treatment the subject receives should be examined to determine whether any of them might have caused the event in question.
- Known response pattern for this class of drug: Clinical/preclinical
- Exposure to physical and/or mental stresses: The exposure to stress might induce adverse changes in the recipient and provide a logical and better explanation for the event
- The pharmacology and PK of the study treatment: The PK properties (absorption, distribution, metabolism and excretion) of the study treatment, coupled with the individual subject's PD should be considered.
- The assessment is not possible

9.6.1.2.4 Action taken with study treatment

Any action on study treatment to resolve the AE is to be documented using the categories listed below.

The study treatment action should be recorded separately for each study treatment as detailed in the eCRF.

- Drug withdrawn
- Drug interrupted
- Dose reduced
- Dose not changed
- Dose increased
- Not applicable
- Unknown

9.6.1.2.5 Other specific treatment(s) of adverse events

- None
- Remedial drug therapy

03 NOV 2020

Version 11.0

Page: 71 of 259

– Other

9.6.1.2.6 Outcome

The outcome of the AE is to be documented as follows:

- Recovered/resolved
- Recovering/resolving
- Recovered/resolved with sequelae
- Not recovered/not resolved
- Fatal
- Unknown

9.6.1.3 Assessments and documentation of adverse events

Once informed consent/assent is obtained during part 1, all AEs occurring through the end of the part 1 follow-up phase will be recorded on the applicable eCRF pages. After the part 1 follow-up phase through the end of the part 2 follow-up phase, only AEs considered at least possibly related to nifurtimox and those caused by protocol-related procedures should be recorded.

No study drug will be administered during part 2. For subjects requiring further treatment with antitrypanosomal drugs, including retreatment with nifurtimox during part 2, the applicable national reporting system should be followed for any spontaneous non-serious and serious adverse reaction considered to be not related to the study medication administered in part 1 (nifurtimox and/or placebo).

After the end of the part 2 follow-up phase, there is no requirement to actively collect AEs, including those having an outcome of "death." The type of information that should be assessed and recorded by the investigator for each AE is listed in Section 9.6.1.2.

"Death" should not be recorded as an AE on the AE page. Instead, "death" is the outcome of underlying AE(s).

For all SAEs, the sponsor has to carry out a separate assessment for expectedness, seriousness, and causal relationship to study drug.

9.6.1.4 Reporting of serious adverse events

The definition of SAEs is given in Section 9.6.1.1. Each SAE must be followed up until resolution or stabilization by submission of updated reports to the designated recipient in part 1 of the study. In part 2, only SAEs considered at least possibly related to nifurtimox or caused by protocol-related procedures must be reported. These events must be followed up until resolution or stabilization by the submission of updated reports to the designated recipient and in accordance with local regulations.

	Integrated Clinical Study Protocol	
	BAY A2502/ 16027	
03 NOV 2020	Version 11.0	Page: 72 of 259

Investigator's notification of the sponsor

All investigators will be thoroughly instructed and trained on all relevant aspects of the investigator's reporting obligations for SAEs. This information, including all relevant contact details, is summarized in the investigator site file. This information will be updated as needed.

The investigator must report immediately (within 24 hours of the investigator's awareness) all SAEs occurring during the observation period defined in Section 9.6.1.3 to the recipient detailed in the instructions for SAE reporting included in the Investigator File. For this, an AE page in the eCRF as well as the complementary pages provided in the Investigator File must be completed for each SAE.

SAEs occurring after the protocol-defined observation period will be processed by the sponsor according to all applicable regulations.

Notification of the IECs/IRBs

Notification of the International Ethics Committees (IECs)/Institutional Review Boards (IRBs) about all relevant events (e.g., SAEs, SUSARs) will be performed by the sponsor and/or by the investigator according to all applicable regulations and IEC/IRB procedures.

Notification of the authorities

The processing and reporting of all relevant events (e.g., SAEs, SUSARs) to the authorities will be done by the sponsor according to all applicable regulations.

Sponsor's notification of the investigational site

The sponsor will inform all investigational sites about reported relevant events (e.g., SUSARs) according to all applicable regulations.

9.6.1.5 Expected adverse events

For this study, the applicable reference document is the most current Investigators' Brochure for nifurtimox.¹⁶⁷

If relevant new safety information is identified, the information will distributed to all participating sites.

The expectedness of AEs will be determined by the sponsor according to the applicable reference document and according to all local regulations.

9.6.1.6 Adverse events of special safety interest

In this study, all AEs of weight loss of > 20%, severe rash, and severe polyneuropathy will be considered AEs of special safety interest.¹⁶⁸ Adverse events of special safety interest will be assessed, monitored, and reported as described in Section 9.6.1.4.

¹⁶⁷ Revised since Investigators' Brochure became available to serve as the reference document for nifurtimox (Amendment 1)

03 NOV 2020 Version 11.0

9.6.2 Pregnancies

Part 1 (CHICO)

Any subject who becomes pregnant during the course of the study will discontinue study treatment. Pregnancy must be confirmed by serum pregnancy test. The investigator must report to the sponsor any pregnancy occurring in a female study subject during her participation in this study. The outcome of the pregnancy should be followed up carefully, and any outcome of the mother and the child at delivery should be reported.

For a pregnancy in the partner of a male study subject, all efforts will be made to obtain similar information on course and outcome, subject to the partner's consent and any abnormal outcome of the child should be reported.

For all reports, the forms provided are to be used. The investigator should submit them within the same timelines as an SAE.

Part 2 (CHICO SECURE)

At each visit in part 2, female subjects will be asked if she is pregnant or gave birth to a baby after the first dose of nifurtimox treatment regimen or since the last visit.

The investigator must report to the sponsor any pregnancy occurring in a female study subject during her participation in this study. The outcome of the pregnancy should be followed up carefully, and any outcome of the mother and the child at delivery should be reported.

Female subjects who give birth by the end of part 2 of the study will be invited to test their child for the absence or presence of infection with *T. cruzi*, except if the child was already tested according to the standards of the country or has already received treatment for Chagas' disease. The congenital infection will be confirmed by parasitological method in children ≤ 8 months of age and by serological method in children >8 months of age. Efforts should be made to obtain the results of congenital infection testing when already done according to the standards of the country. The result of congenital infection will be documented in the applicable eCRF form.

9.6.3 Further safety

9.6.3.1 Laboratory assessments

Safety laboratory assessments will be performed at screening, Visits 3, 6, 8 (EOT), and 9 (follow-up). Fasting is dependent on the age of the subject at the discretion of the investigator. If any abnormal laboratory values occur at the EOT Visit (Visit 8), these determinations will be followed until normal or stable.¹⁶⁹

Laboratory parameters will be analyzed by a local laboratory according to the schedule specified in Table 9–4: .

¹⁶⁸ Sentence corrected as per amendment 3

¹⁶⁹ Heading 9.6.3.1 added; text modified for clarity and to reflect changes made per Amendment 1.

|--|

Table 9–4:	Description	of laboratory	parameters	(safety)
------------	-------------	---------------	------------	----------

Hematology	Hemoglobin, hematocrit, RBC count, WBC count and differential (including lymphocytes, monocytes, eosinophils, basophils, neutrophils), MCV, MCH, MCHC, platelets
Blood chemistry	Albumin, total protein, BUN, creatinine, glucose, total bilirubin, ALP, AST, ALT, uric acid
Coagulation	INR, PT, PTT
Urinalysis (urine dipstick) a	RBCs, WBCs, pH, specific gravity, glucose, protein, bilirubin, urobilinogen, nitrite, ketones
Urine pregnancy test ^b	Urine β-hCG

Page: 74 of 259

ALP = alkaline phosphatase, ALT = alanine aminotransferase, AST = aspartate aminotransferase, β-hCG = beta-human chorionic gonadotropin, BUN = blood urea nitrogen, INR = international normalized ratio, MCV = mean corpuscular volume, MCH = mean corpuscular hemoglobin, MCHC = mean corpuscular hemoglobin concentration, PT = prothrombin time, PTT = partial thromboplastin time, RBC = red blood cell, WBC = white blood cell.

 a If abnormalities are identified by the dipstick, the samples will be sent for confirmatory testing¹⁷⁰. Cell/sediment microscopy should be performed only if positive dipstick results are obtained for WBC, RBC/hemoglobin, or protein.

b To be performed at Visits 1, 2, 3, 6, 8, and 9 on females of childbearing potential (i.e., female subjects who have experienced menarche). If any urine pregnancy test is positive, a serum pregnancy test will be performed to confirm the result.¹⁷¹

Safety laboratory assessments are not applicable in part 2 of the study.

9.6.3.2 Total volume of blood

In order to minimize the burden of blood loss due to PK sampling, age-appropriate sparse sampling strategies combined with (micro-)bioanalysis techniques will be applied. The total volume of blood obtained at each visit (for serology, qPCR, safety, and PK specimens) will be a maximum of approximately 8.1 mL 15.6 mL depending on the child's age and weight as per standards of Clinical Laboratory and Standards Institute; see Section 16.6 and Table 9–5 below.¹⁷²

Age	Weight	Circulating blood volume	Maximum allowable every two weeks
Pre-term neonate	500 grams	40 mL	1.5 mL
Full-term neonate	4 kilograms	320 mL	12 mL
Infant (3 years)	15 kilograms	1.2 L	45 mL
Child (12 years)	40 kilograms	3.2 L	120 mL

Table 9–5: Total volume of blood by age

¹⁷⁰ Modified as per amendment 2

¹⁷¹ Text modified to reflect changes made per Amendment 1

¹⁷² Text modified for clarity and to expand the maximum amount of blood required (Amendment 1)

03 NOV 2020 Version 11.0

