9.2 Visit description

9.2.1 Screening

9.2.1.1 Visit 1 – screening visit (Days -14 to -1)

No study-specific procedures will be performed before the subject/legally authorized representative signs the informed consent form, or a minor subject provides assent, including asking a potential subject to fast (if applicable, depending on the age of the subject at the discretion of the investigator) prior to the screening blood samples. Informed consent/assent for optional PK blood sampling will also be obtained. After the consents/assents have been obtained, the following assessments will be performed:

- Collection of demographic data
- Medical and surgical history, including date of menarche for female subjects, and method of contraception
- Evaluation of inclusion and exclusion criteria
- Assessment of Chagas' disease signs and symptoms (to be performed during physical examinations); see Section 9.4.4
- Concentration test for *T. cruzi* (subjects <8 months of age at randomization) and conventional serologic testing for Chagas' disease (subjects ≥ 8 months < 18 years of age) conducted in local laboratory (or acceptable documentation of positive Chagas' disease within 3 months prior to screening and no prior anti-trypanocidal or anti-parasitic treatment). Specimens taken for conventional serology, non-conventional serology, IHA, and qPCR will be frozen and stored at -20°C prior to shipment to the central laboratory where they will be stored at -70°C.^{117,118}
- Assessment of pretreatment AEs and concomitant medications
- A complete physical examination of body systems. Abnormal findings will be documented as medical history (see Section 9.6.1.1).
- Neurological examination (see Section 9.6.3.3). Abnormal findings will be documented as medical history (see Section 9.6.1.1).
- Vital signs (blood pressure is optional in subjects < 5 years of age at the discretion of the investigator), height/length, and weight
- 12-lead ECG (optional in subjects < 5 years of age at the discretion of the investigator)
- Serum hematology and chemistry, coagulation, and urinalysis (if urine specimen can be obtained). Fasting is dependent on the age of the subject at the discretion of the investigator.

¹¹⁷ Modified as per Amendment 2 and Amendment 5.

¹¹⁸ Replaced IFA with IHA per Amendment 6.

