9.4.2 Serological tests

At screening, subjects must have the following serological tests to confirm a diagnosis of Chagas' disease:

- Subjects < 8 months of age at randomization must demonstrate direct observation of *T. cruzi* by concentration test¹⁴⁹
- Subjects ≥ 8 months to < 18 years of age at randomization must demonstrate a positive conventional ELISA result for both of the following tests to confirm diagnosis:
 - Recombinant ELISA
 - Total purified antigen ELISA¹⁵⁰

Additionally, a non-conventional ELISA test and IHA will be obtained; however, a positive result will not be required for diagnosis^{151,152}.

Subjects will also be eligible if there is acceptable documentation of positive Chagas' disease within 3 months prior to screening and they have had no prior anti-trypanocidal or anti-parasitic treatment.¹⁵³

After randomization, conventional and non-conventional serological tests will be performed at Visits 3, 6, and 8 (EOT), and Visits 10 and 11 (Follow-up).¹⁵⁴

All subjects ≥ 8 months to < 18 years of age at randomization will have two baseline specimens collected for serologic testing. One sample will be used to determine the initial diagnosis of Chagas' disease while the other sample will be frozen and retained to be assayed later as an internal control. Subjects < 8 months of age at randomization will have one specimen obtained, which will be frozen and retained. Total blood volume to be taken for the

¹⁴⁸ Modified as per amendment 2

¹⁴⁹ Text modified for clarity (Amendment 1)

¹⁵⁰ Text modified for clarity and per Modification 2 (Amendment 1)

¹⁵¹ IFA test added per Amendment 5.

¹⁵² Replaced IFA with IHA per Amendment 6.

¹⁵³ Text modified/added for clarity and per Modification 2 (Amendment 1)

¹⁵⁴ Text modified for clarity and to reflect changes per Amendment 1

	Integrated Clinical Study Protocol BAY A2502/ 16027
03 NOV 2020	Version 11.0

required three serological and PCR tests is 4.0-5.0 mL, depending on the subject's age. Care will be taken to minimize sample volumes by using a micro-sampling collection technique, when possible.¹⁵⁵

Page: 63 of 259

Details describing the collection, processing, storage and shipment of blood samples, and the serologic test protocols, will be described in a separate serologic test manual from the central laboratory.

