9.5 Pharmacokinetics/pharmacodynamics

If the subject/subject's legally authorized representative(s) provide(s) consent/assent to do so, plasma concentrations of nifurtimox will be evaluated at Visit 2 (baseline) and Visits 3, 6, and 8 (EOT) on at least 10 subjects per age stratum should be selected from all participating PK centers. Plasma nifurtimox concentrations will be determined using a sparse sampling approach.¹⁵⁸

At Visits 2, 3, 6, and 8, the subjects should present themselves to the investigational site without taking the morning dose of study medication. Blood samples for PK will be obtained in-clinic prior to the administration of study drug with food and at specific time points and time windows as presented in Table 9–1. At the 2 – 4 hour time point of PK blood sampling (i.e., at the time of C_{max}), an ECG (optional for subjects < 5 years of age at the discretion of the investigator) will be obtained to allow for PK/PD investigations.¹⁵⁹ All subjects are to complete the PK subject diary according to instructions provided.¹⁶⁰

PK/PD investigation is not applicable in part 2 of the study.

¹⁵⁸ Text modified for clarity and per Amendment 1

¹⁵⁹ Text modified for clarity and per Modification 1 (Amendment 1)

¹⁶⁰ Text modified as per amendment 4

03 NOV 2020 Version 11.0

Page: 66 of 259

Table 9–3:	: Pharmacokinetic sampling time points and windows ¹⁶¹
------------	---

Visits (Days)	Time point	Time window
2, 3, 6, 8 (1, 7, 30, 60)	Pre-dose (pre-treatment)	
	Post-dose	5-10 minutes post-dose
		10-120 minutes post-dose
		2-4 hours post-dose ^a
		4-8 hours post-dose

a An ECG will be obtained at this time point (optional in subjects < 5 years of age at the discretion of the investigator)

PK blood samples are to be obtained from a heel prick (subjects up to 1 month of age), finger stick, or ear lobe stick at the discretion of the investigator. For all subjects throughout the study, the selected specimen handling technique will be via microsampling in order to provide uniform analytical samples while maintaining total blood volumes within the limitations for safety.

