Samples of a blood volume of 2 x 75 = 150 μ L at predefined time points should be taken according to Table 9–3. If samples cannot be taken due to other reasons (e.g., sampling deemed not feasible by the investigator due to safety) or if the samples are taken outside the defined time windows (e.g., > 8 hours post-dose), the subject will still remain valid for PK analysis. At least one sample within the specified timeframe should be taken during the course of the study. ¹⁶² That means that, at the end of the study, at least one sample from each time window will be available, e.g., if the 4-8 hour post-dose sample was not collected until the last visit, then a sample at this time window should in any case be drawn at that time point. This must be documented by the investigator.

The PK samples should be obtained within the planned sampling time windows unless important or unforeseen mandatory interventions coincide (e.g., for medical reasons).¹⁶³ In these exceptional cases, the corresponding sample may be obtained outside the predefined windows without losing its validity for subsequent PK analysis. This will not be considered as a protocol violation. If a subject fails to provide the number of samples defined in the protocol, this will also not render him/her invalid for the subsequent PK analysis.

Details describing the procedures for obtaining and handling PK blood samples are provided in Section 16.5.

Analysis of PK samples

Nifurtimox concentrations in plasma will be measured by a validated assay using high performance liquid chromatography followed by tandem mass spectrometric detection. Quality control (QC) and calibration samples will be analyzed concurrently with study samples. The results of QC samples will be reported together with concentrations in the study samples in the clinical study report.

¹⁶¹ Visit numbers changed to reflect changes made per Amendment 1; footnote a added per Modification 1 (Amendment 1)

¹⁶² Text modified for clarity (Amendment 1)

¹⁶³ Text modified for clarity (Amendment 1)

	Integrated Clinical Study Protocol BAY A2502/16027	
03 NOV 2020	Version 11.0	Page: 67 of 259

The bioanalyst will remain unblinded for analysis of study samples. Concentrations are calculated from the chromatographic raw data in accordance with current Bayer guidelines [31].

Pharmacokinetic evaluation

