16.6 Maximum blood volumes for pediatric patients – Clinical and Laboratory Standards Institute

Patient's	Patient's	Maximum amount	Maximum cumulative
Weight (lbs)	weight (kg)	to be drawn at any	amount to be drawn
(iss)	weight (kg)	one time (mL)	during a hospital
		one time (init)	stay of 1 month
			or less (mL)
6-8	27.2.6	25	
	2.7-3.6	2.5	23
8-10	3.6-4.5	3.5	30
11-15	4.5-6.8	5	40
16-20	7.3-9.1	10	60
21-25	9.5-11.4	10	70
26-30	11.8-13.6	10	80
31-35	14.1-15.9	10	100
36-40	16.4-18.2	10	130
41-45	18.620.5	20	140
46-50	20.9-22.7	20	160
51-55	23.2-25.0	20	180
56-60	25.5-27.3	20	200
61-65	27.7-29.5	25	220
66-70	30.0-31.8	30	240
71-75	32.3-34.1	30	250
76-80	34.5-36.4	30	270
81-85	36.8-38.6	30	290
86-90	39.1-40.9	30	310
91-95	41.1-43.2	30	330
96-100	43.6-45.5	30	350

* For patients that weigh less than 6 lbs, consult physician

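### The lowest per-visit blood maximum (about 8.1 mL) does not fit the single-draw limits it cites for infants of 2.7 to 6.8 kg

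*Protocol*

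**What the plan says.** Section 9.6.3.2 of the protocol sets the total blood per visit for serology, qPCR, safety and PK specimens. It "will be a maximum of approximately 8.1 mL 15.6 mL depending on the child's age and weight"; the two figures are read here as the ends of a range. The same sentence says that the volume follows a laboratory-standards body and points to Section 16.6 and Table 9-5.

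- **Section 16.6** gives, by weight, the most that may be drawn at one time and cumulatively over a month. The three lightest bands are 2.7-3.6 kg (2.5 mL; 23 mL), 3.6-4.5 kg (3.5 mL; 30 mL) and 4.5-6.8 kg (5 mL; 40 mL). Its footnote reads: "For patients that weigh less than 6 lbs, consult physician".
- **Table 9-5** has a column headed "Maximum allowable every two weeks", with 12 mL for a 4 kg full-term neonate.
- **Section 9.4.2** says that the volume for the "required three serological and PCR tests is 4.0-5.0 mL, depending on the subject's age". It adds that care "will be taken to minimize sample volumes by using a micro-sampling collection technique", but only where possible.
- **Section 9.5** describes PK samples: "Samples of a blood volume of 2 x 75 = 150" microlitres per time point. Table 9-3 lists one pre-dose time and four post-dose windows, the last being "4-8 hours post-dose".

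Infants this small are in scope. Stratum 1 starts at day 0, the birth-weight exclusion in Section 6.2 is below 2500 g, and the dosing in Table 7-2 starts at 2.5 kg.

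**The concern.** Section 9.6.3.2 is the blood-volume ceiling that sites and ethics committees will read. No per-visit maximum below about 8.1 mL is given for any child, yet the standard cited for that figure allows much less at one time in the lightest infants.

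Two practical problems follow. A site working from 9.6.3.2 alone could take more from a 3 kg infant in one draw than Section 16.6 permits. A site working from Section 16.6 finds that 4.0 mL of serology and PCR blood does not fit one draw below 4.5 kg, and it is not told what to reduce, split or omit. The question arises at screening and at Visits 3, 6 and 8. It does not arise at Visit 2 (PK blood only) or at Visit 9 (no serology, qPCR or PK blood).

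**Working it through.** **Inputs.** Lowest per-visit maximum 8.1 mL (9.6.3.2); single-draw and monthly limits (16.6); serology plus PCR 4.0 mL at the lower end (9.4.2); PK 0.150 mL at each of 5 time points (9.5, Table 9-3); two-week limits (Table 9-5).

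**Can 8.1 mL be rebuilt?** No, because the volume for safety tests is not stated. PK blood is 5 x 0.150 = 0.75 mL per PK visit. If the 8.1 mL contains 4.0 mL of serology and PCR blood and all the PK blood, then 8.1 - 4.0 - 0.75 = 3.35 mL is left for safety tests. That figure is an inference.

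**One draw against Section 16.6** (ratio = volume / single-draw limit). The volume without PK is 8.1 - 0.75 = 7.35 mL, which assumes that 8.1 mL includes all five PK samples.

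| Weight (kg) | Limit (mL) | 8.1 mL | 7.35 mL (no PK) | 4.0 mL (serology + PCR) |
|---|---|---|---|---|
| 2.7-3.6 | 2.5 | 3.24 | 2.94 | 1.60 |
| 3.6-4.5 | 3.5 | 2.31 | 2.10 | 1.14 |
| 4.5-6.8 | 5 | 1.62 | 1.47 | 0.80 |
| 7.3-9.1 | 10 | 0.81 | 0.74 | 0.40 |

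The mismatch is confined to the three lightest bands. Setting aside the PK blood, the only blood that the protocol spreads over time, does not remove it. At 2.5 mL per draw, 7.35 mL would need three draws.

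**One visit against the other limits.** 8.1 mL is below the monthly limits of 23, 30 and 40 mL. Every row of Table 9-5 works out at 3 mL/kg per two weeks (1.5/0.5 = 12/4 = 45/15 = 120/40 = 3), so one 8.1 mL visit fits from 8.1/3 = 2.7 kg.

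**Two visits against Table 9-5 (worst case, secondary).** Screening is Visit 1, the "screening visit (Days -14 to -1") window, and Visit 3 is on Day 6 to 8. Screening on Day -6 to Day -1 falls 6 to 13 days before Visit 3. Assume that both visits reach the ceiling and that the ceiling at screening is 8.1 mL less PK:

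- With PK: 7.35 (screening) + 0.75 (Visit 2 PK) + 8.1 (Visit 3) = 16.2 mL. Against 12 mL at 4 kg, 16.2/12 = 1.35. At 3 mL/kg the limit is met from 16.2/3 = 5.4 kg.
- Without PK: 2 x 7.35 = 14.7 mL; 14.7/12 = 1.225; the limit is met from 14.7/3 = 4.9 kg.

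**The case against.** The strongest reply is that two different quantities are being compared. Section 9.6.3.2 gives a visit total, Section 16.6 limits one draw, and nothing says that a visit's blood is taken at once. That is correct, so the ratios are conditional on a single draw.

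The second reply is that the sentence in 9.6.3.2 already brings in the standard, so an over-limit draw would breach the protocol itself. Section 9.5 also commits to micro-sampling within safe total volumes, although that passage is written for PK specimens. This has force, but it does not settle the matter. If Section 16.6 governs, the stated lower end is not usable as one draw in these infants, and the 4.0 mL in 9.4.2 still exceeds the two lightest limits.

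The third reply is that several components are inferred. This stands. The safety-test volume is not given, and 9.4.2 takes one baseline specimen rather than two below 8 months. Whether the 4.0 mL already reflects that is not stated. Collection details sit in a central-laboratory manual that was not available. The two-week total also needs a short screening interval and the ceiling at both visits, so it is a worst case only.

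A reader might infer that the protocol plans to draw about three times the permitted volume from newborns, or that it breaches Table 9-5. The documents support neither reading. They state a maximum, make it depend on age and weight, and cite the limits in the same sentence.

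**Conclusion.** The point holds as a mismatch between a stated safety ceiling and the standard cited for it. For infants of 2.7-3.6, 3.6-4.5 and 4.5-6.8 kg, the lowest per-visit maximum is 3.2, 2.3 and 1.6 times the single-draw limit if taken in one draw. The lower end for serology plus PCR is 1.6 and 1.1 times the two lightest limits and fits the third. The protocol describes no splitting apart from the PK micro-samples.

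The comparison with Section 16.6 uses only stated figures and the single-draw condition. The two-week excess (about 15 to 16 mL against 12 mL at 4 kg) rests on further assumptions and is secondary. Infants under 8 months also have concentration tests, which the specimen list in 9.6.3.2 does not name; their volume is not stated and is not counted here.

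Severity is minor to moderate, with medium confidence about the practical effect. The point concerns Part 1 draws in young infants, and the analysis of the 12-month primary endpoint is unchanged.

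**What to change.** In Section 9.6.3.2:

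- Keep a per-visit cap. Replacing it with per-draw limits alone would let repeated draws exceed it: at 4 kg, three draws of 3.5 mL make 10.5 mL and still fit the 12 mL two-week limit.
- Add the Section 16.6 per-draw maxima for infants below 6.8 kg: 2.5, 3.5 and 5 mL by band, with physician consultation below 6 lbs.
- State that the Section 16.6 per-draw limits and the Table 9-5 two-week limit take precedence over the per-visit figure.

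In Section 9.4.2, state that below 6.8 kg the serology and PCR volume is reduced, or split across draws, to stay within the limit. There is room for this, because the suggested qPCR procedure in Section 16.4 accepts a minimum of 1 mL up to 12 months of age.

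The cost is a short protocol clarification and a matching laboratory-manual update. Some samples in the lightest infants may be smaller, split or lost, with some missing qPCR or serology results. The documents do not say whether infant sampling in Part 1 was still open at version 11.0. If it was finished, the useful step is to correct the text and check the infant draws already taken against Section 16.6.
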